This approval is issued under Colorado State University's Federal Wide Assurance 00000647 with the Office for Human Research Protections (OHRP). If you have any questions regarding your obligations under CSU's Assurance, please do not hesitate to contact us.

Please direct any questions about the IRB's actions on this project to:

IRB Office - [contact]; [contact]
[name], Senior IRB Coordinator - [contact]; [contact]
[name], IRB Biomedical Coordinator - [contact]; [contact]

[name]

Continuing renewal has been reviewed at the convened meeting on March 22, 2018. Continuation has been approved to recruit the remaining participants with the approved recruitment and consent procedures. This renewal acknowledges an

Research Integrity & Compliance Review Office
Office of the Vice President for Research
[name] eprotocol
[contact]
[contact]

error in the initial approval letter generated by the IRB in that it should have stated approval for recruitment of 60 participants. This renewal includes two deviation reports that were assessed and two proposed amendments in response to the reports. These amendments include expanding enrollment to include participants with 10-day course of antibiotics with medical monitor support and increased enrollment a total of 200 participants. This number is to ensure participants completing the study will amount to 60 individuals. This is in response to large number of screen fails and withdrawals. Approved documents include: Consent, version dated 01March2018.

Approval Period: March 22, 2018 through March 21, 2019
Review Type: FULLBOARD
IRB Number: 00010468
Funding: AstraZeneca

Continuing review.....	1
Personnel Information.....	3
Subject Population.....	6
Study Location.....	7
General Checklist.....	7
Funding.....	9
Expedited Paragraphs.....	10
Purpose, Study Procedures, Background.....	12
Radioisotopes or Radiation Machines.....	19
Medical Equipment for Human Subjects and Laboratory Animals; Investigational Devices.....	20
Drugs, Reagents, or Chemicals.....	20
Subject Population (a-g).....	21
Subject Population (h-m).....	24
Risks.....	27
Benefits, Procedures to Maintain Confidentiality.....	32
Potential Conflict of Interest.....	33
Informed Consent.....	34
Assent Background.....	35
HIPAA.....	35
Attachments.....	37
Obligations.....	42

Event History.....	43
--------------------	----

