*** Purpose, Study Procedures, Background ***

Original Protocol Number (e.g., 07-226H)

Cloned and subsequently modified from 14-5531H

Title (Please indicate if the protocol title is different from the proposal title)

Does Dapagliflozin Provide Additional Health Benefits To Dietary Counseling For Weight Loss?
Clinical Research Protocol Title: Dapagliflozin Promotes Favorable Health Benefits That Are Independent Of Weight Loss In Overweight/Obese Adults

Complete Sections 1 - 16. Specify N/A as appropriate. Do not leave any required sections blank.

1. Purpose of the study

a) Provide a brief lay summary of the project in <200 words. The lay summary should be readily understandable to the general public, and is, for example, what would be released to a newspaper if requested.

THIS PROTOCOL IS AN AMENDED/SIMPLIFIED VERSION OF IRB PROTOCOL 14-5531H.

Dapagliflozin is a medicine to treat diabetes. Its mechanism of action is via sodium-glucose co-transporter 2 (SGLT2) inhibition. In adults with diabetes, use of sodium-glucose co-transporter 2 inhibitors is associated with moderate weight (fat) loss, in addition to other health benefits, including decreased blood pressure, decreased inflammation, and decreased oxidative stress. It is unclear as to whether these health

Protocol Title: Does Dapagliflozin Provide Additional Health Benefits To Dietary Counseling For Weight Loss?
Clinical Research Protocol Title: Dapagliflozin Promotes Favorable Health Benefits That Are Independent Of Weight Loss In Overweight/Obese Adults

Protocol Type: Biomedical

Date Submitted: 03/01/2018

Approval Period: Draft

Important Note: This Print View may not reflect all comments and contingencies for approval. Please check the comments section of the online protocol.
Questions that appear to not have been answered may not have been required for this submission.
Please see the system application for more details.

benefits are due to SGLT2 inhibition per se, or as a secondary effect of weight loss. We wish to compare the health benefits of dietary counseling for weight loss with and without concomitant use of an SGLT2 inhibitor.

b) What does the Investigator(s) hope to learn from the study?

We wish to learn if:

1. Dapagliflozin (SGLT2 inhibition) provides additional health benefits to dietary counseling for weight loss?

and if,

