2. Weight loss associated with dietary counseling and the use of Dapagliflozin (SGLT2 inhibition) is characterized by normal circulating satiety signals rather than the usual diet-induced changes in circulating peptides that increase hunger and reduce satiety.

c) Proposed Start Date (may not precede IRB approval date):

On receipt of IRB approval.

2.

Study Procedures (If this is a student project, the methods section of the thesis or dissertation proposal must be attached in section #16 - Attachment section.)

a) In lay language, describe all the procedures, from screening through end-of-study, that the human subject must undergo in the research project, including study visits, drug treatments, randomization and the procedures that are part of standard of care. Please note: Do NOT respond "See Attachment Section." If you would like to add tables, charts, etc., attach those files in the Attachment section (#16).

OVERVIEW

This is a randomized, prospective, placebo-controlled, double blind, repeated measures study. 60 overweight/obese adults (body mass index > 27.5 kg/m²) will be recruited for participation and randomly assigned to one of two 12 week treatments: (1) daily oral administration of Dapagliflozin with dietary counseling to promote weight loss; or, (2) daily oral administration of a placebo with dietary counseling to promote weight loss.

Study participants will report to the research facilities on the Colorado State University main campus on 29 separate occasions:

Visit 1: study participants will undergo screening: medical history, 12-lead electrocardiogram and blood pressure assessment at rest and during incremental exercise to volitional exhaustion, blood sampling, and measurement of body composition.

Visit 2: an oral glucose tolerance test will be performed and resting metabolic rate and blood pressure will

Protocol Title: Does Dapagliflozin Provide Additional Health Benefits To Dietary Counseling For Weight Loss?
Clinical Research Protocol Title: Dapagliflozin Promotes Favorable Health Benefits That Are Independent Of Weight Loss In Overweight/Obese Adults

Protocol Type: Biomedical

Date Submitted: 03/01/2018

Approval Period: Draft

Important Note: This Print View may not reflect all comments and contingencies for approval. Please check the comments section of the online protocol.
Questions that appear to not have been answered may not have been required for this submission.
Please see the system application for more details.

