Aside from the metabolic benefits pertaining to glucose control, inhibition of sodium-glucose co-transporter 2 (SGLT2) in patients is associated with moderate weight loss (Tahrani et al., 2011; Chen & Leung, 2013), with some studies reporting up to 4.5 kg decreases in body mass over 12 weeks (Wilding et al., 2009). Animal data are consistent with these observations (Devenny et al., 2012; Liang et al., 2012). SGLT2 inhibition is also associated with other health benefits, including decreased blood pressure (Ferrannini et al., 2010; Dobbins et al., 2012), decreased inflammation (Chen et al., 2012; Tahara et al., 2013, 2014), and decreased oxidative stress (Tahara et al., 2013, 2014)—all health benefits with very important implications for improved physiological function and decreased disease-risk. At present, it is unclear as to whether these health benefits are due to SGLT2 inhibition per se, or as a secondary effect of weight loss.

Noteworthy, the weight loss observed in patients associated with SGLT2 inhibition is not mediated by intentional dietary restriction/intervention. It is more likely to be mediated by the caloric loss associated with the decreased renal tubular reabsorption of glucose, leading to urinary glucose excretions ranging between 45 and 80 g/day (180-320 kcal/d), depending on the drug dose (Idris & Donnelly, 2009). This caloric deficit is not trivial. Typically, caloric deficits of this magnitude require either increased physical activity and/or dietary restriction.

In our original study (Protocol 14-5531H) we learned that when adults with normal, healthy glucose control use SGLT2 inhibitors, the weight loss is negligible. Nevertheless, even in healthy adults, SGLT2 inhibition leads to glucose spillage into urine that may elicit other, non-weight loss mediated health benefits. Therefore in the current project we will study the use of SGLT2 inhibitors combined with dietary counseling for weight loss.

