Baseline (pre-counselling) differences between placebo and SGLT2 inhibition groups were compared using independent Student t-Tests. Consistent with the experimental design (randomized, double-blind, parallel, repeated measures) the influence of SGLT2 inhibition on the physiological responses to dietary counselling was examined using two-way (group: placebo vs. SGLT2 inhibition x time: before vs. after dietary counselling) analysis of variance (ANOVA). The influence of SGLT2 inhibition and dietary counselling on the dynamic responses to oral glucose ingestion were examined using three-way ANOVA (placebo vs. SGLT2 inhibition x before vs. after dietary counselling x time points during the OGTT). Pairwise multiple comparison procedures were performed using the Holm-Sidak Method. Relations of interest were described using Pearson product-moment correlations. The level of statistical significance was set at $P<0.05$. Data are reported as mean and standard deviation, unless otherwise indicated. Calculations were performed using commercially available statistical software (SigmaStat 3.0, Systat Software Inc., San Jose, California, USA).

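### The SAP's Pearson correlations carry no arm term and leave pooling unstated; if the arms are pooled and the drug moves both variables, arm alone can create or distort a correlation

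*Combined protocol and SAP*

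**What the plan says.** The SAP gives association between variables one sentence: "Relations of interest were described using Pearson product-moment correlations". It does not list the variables, say whether levels or changes are used, or state how treatment arm or the two measurement occasions are handled.

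The sentence that follows applies to the whole plan: "The level of statistical significance was set at $P<0.05". Nothing exempts the correlations from it.

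Arm does appear elsewhere in the SAP, in the group-by-time ANOVA and in the three-way ANOVA for the glucose tolerance test. Neither contains change in weight or any other outcome as a covariate.

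Protocol section 1(a) says it is unclear whether the "benefits are due to SGLT2 inhibition per se, or as a secondary effect of weight loss". Section 3(a) repeats this, and the clinical protocol title asserts benefits that do not depend on weight loss. Section 2(a) describes 60 adults who "will be recruited for participation and randomly assigned to one of two 12 week treatments". The IRB approval letter explains the larger enrolment of 200: "This number is to ensure participants completing the study will amount to 60 individuals".

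**The concern.** In a two-arm trial, a correlation over all participants has two sources: how the variables move together among people on the same treatment, and how the arm means differ. If the drug lowers two outcomes by separate routes, treated participants sit lower on both. The pooled scatter then slopes even though neither outcome says anything about the other within an arm.

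Correlation is the only method in the SAP that relates one outcome to another. If it were applied to weight change and a health benefit, a pooled coefficient could suggest a link that comes only from both having responded to the drug. The same could happen with any other pair that the drug moves together, such as glucose and insulin.

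A lesser gap is that the design is before-and-after and the sentence does not limit input to one pair per participant. Entering both occasions would count correlated observations as independent.

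**Working it through.** The plan has no figure to reproduce: it states no effect size, SD, correlation or power. The check asks how large the artefact could be.

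**Inputs**
- From the documents: 60 completers in two arms; significance level 0.05.
- Assumed: 1:1 allocation (30 per arm), a two-sided test, normal variables with unit within-arm SD, and drug shifts d1 and d2 in SD units.

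**Expected pooled correlation.** With equal arms, the arm difference adds d²/4 to each variance and d1·d2/4 to the covariance. With within-arm correlation ρ:

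r = (ρ + d1·d2/4) / √[(1 + d1²/4)(1 + d2²/4)]

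Setting ρ = 0:
- 0.5 and 0.5: 0.0625/1.0625 = 0.059
- 0.8 and 0.8: 0.16/1.16 = 0.138
- 1.0 and 1.0: 0.25/1.25 = 0.200
- 0.2 and 0.8: 0.04/√(1.01 × 1.16) = 0.037
- either shift zero: 0

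Shifts in opposite directions give the same size with a negative sign. If ρ is not zero, the coefficient is distorted. Taking ρ = 0.30 for illustration, shifts of 0.8 in both give 0.46/1.16 = 0.40, and shifts of 0 and 0.8 give 0.30/√1.16 = 0.28.

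**Critical value.** At n = 60 (58 df) the two-sided 5% limit for |r| is 0.254. The expected r reaches it only when both shifts are about 1.17 SD (r = 0.255).

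**Rejection rates with ρ = 0** (40,000 simulated trials per row; adjusted test on 57 df):

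| Shifts (SD) | Pooled, P<0.05 | Arm-adjusted, P<0.05 |
|---|---|---|
| 0 and 0.8 | 0.051 | 0.051 |
| 0.2 and 0.8 | 0.057 | 0.048 |
| 0.5 and 0.5 | 0.074 | 0.050 |
| 0.5 and 0.8 | 0.106 | 0.051 |
| 0.8 and 0.8 | 0.187 | 0.051 |
| 1.0 and 1.0 | 0.343 | 0.050 |

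A separate run of 200,000 trials gave pooled rates of 0.058 at 0.2 and 0.8, 0.073 at 0.5, 0.185 at 0.8 and 0.341 at 1.0.

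For scale, 30 per arm has about 80% power for a shift of 0.72 to 0.73 SD in a single outcome.

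**Both occasions entered as 120 points.** Take two unrelated variables, no drug or counselling effect, and an assumed before-after correlation c in each. The variance of r is inflated by about 1 + c², so the false-positive rate is about 2·[1 − Φ(1.96/√(1 + c²))]. For c = 0.5, 0.7, 0.8 and 0.9 this gives 8%, 11%, 13% and 14.5%. Simulation gave 8%, 11%, 13% and 15%.

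**The case against.** A reader might infer that the trial will correlate weight loss with its benefits across pooled arms, that these must come out correlated, and that the result will be read as a weight-linked benefit. The documents do not support that reading.

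- **Pooling is not stated.** Separate correlations by arm fit the SAP's wording equally well.
- **No pair involving weight is named.** The verb is descriptive, and nothing says that a coefficient will be taken as evidence of mediation.
- **The artefact needs a drug effect on both variables.** For weight, section 3(a) reports from the original study that "when adults with normal, healthy glucose control use SGLT2 inhibitors, the weight loss is negligible". The counselling in section 2(a) also steers participants towards a target weight, which may narrow any arm difference, although matched targets are not stated. With a small weight effect, as in the 0.2 and 0.8 SD row, the rate is close to nominal.
- **The direction is not fixed.** A spurious positive link needs both variables to move the same way. For weight pairs, such a link would count against the titled hypothesis, not for it.
- **The main aims are comparisons between arms.** The group-by-time ANOVA contains arm and addresses them.

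All of this stands, and it limits the point to a conditional one. It does not remove it. The negligible weight loss was seen with the drug in the original study, and no figure is given for drug plus counselling. Pairs other than weight may both respond to the drug. The 0.05 threshold is not withheld from the correlations. The text also permits either a confounded analysis or an unconfounded one, with the choice open until the data are seen. Entering both occasions is likewise only something the wording allows; nothing suggests it was intended.

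**Conclusion.** The point holds conditionally. The SAP names plain Pearson correlation without saying how arm or repeated measurement is handled. If the arms are pooled and the drug moves both variables, arm alone can create or distort a correlation.

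The inflation is slight at 0.5 SD in both variables and substantial only from about 0.8 SD in both. It is negligible when one effect is small and absent when one is zero. The sizes rest on equal arms, a two-sided test, zero within-arm correlation and assumed shifts; none of these is a document figure.

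The gap bears on whether benefits are secondary to weight loss, but neither a pooled nor an adjusted correlation answers that question. That no analysis in the SAP adjusts an outcome for weight change is a separate matter, which this point does not resolve. Severity is minor; this is a cheap improvement.

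**What to change.** Replace the SAP's correlation sentence with:

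> Relations between before-to-after changes are estimated as partial correlations adjusted for treatment arm (equivalently, regression with arm in the model), one pair per participant, with 95% CI; arm-specific coefficients are shown alongside and are not interpreted as proof of mediation.

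Listing the pairs of interest next to this sentence would complete it.

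The cost is one sentence and one degree of freedom: the critical |r| at n = 60 moves from 0.254 to 0.256. No new data are needed. Under the assumptions above, the adjusted test held its error rate at 0.048 to 0.051 in every scenario. The arm-specific coefficients will be imprecise, because with 30 participants the critical |r| is 0.361. They serve to show whether the relation looks similar in the two arms.
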